# **Experimental Design and Methods**

## Design:

This study will be a multi-center prospective, randomized control trial. After informed and written parental consent, a total of 60 neonates and infants (<12 months) will be enrolled at Children's Healthcare of Atlanta or Lucile Packard Children's Hospital at Stanford Hospital.

### Study Population:

The following criteria will be used to determine patient eligibility: Inclusion Criteria:

- Full term neonates (32-42 weeks gestational age)
- weight  $\geq$  to 3 kg at time of surgery
- Infants less than 12 months of age
- Infants and Neonates undergoing elective cardiac surgery requiring CPB at Children's Healthcare of Atlanta or Lucile Packard Children's Hospital at Stanford Hospital
- No known patient or family history of coagulation defect or coagulopathy
- Parents willing to participate and able to understand and sign the provided informed consent

Exclusion Criteria:

- Preterm neonates (less than 32 weeks gestation)
- Patients less than 3 kg at time of surgery
- Patients >12 months of age
- Patients undergoing emergent procedure
- Patients undergoing cardiac surgery not requiring CPB
- Patients with known coagulation defect or coagulopathy
- Family history of coagulation defect or coagulopathy
- Parents unwilling to participate or unable to understand and sign the provided informed consent

### Enrollment/Consent Process:

The Institutional Review Board will approve informed consent documents prior to commencement of the study. Only those patients who meet the entry criteria will be considered as possible study candidates. Patients will be enrolled consecutively and randomized per protocol as they present to Children's Healthcare of Atlanta.

The parent(s) or legal guardian of the neonate will be approached on a day prior to surgery by the principal investigator, or a member of the IRB approved study team to discuss the goals, benefits and risks of the project. A thorough discussion between the parent(s) or legal guardian and the IRB approved study team will occur during the study consent process. Written informed consent will be obtained following this discussion.

For the occasions when parent(s) or legal guardian does not arrive at the hospital until the day of surgery, they will be approached only if there is sufficient time to allow for their full consideration. No study related procedure will occur prior to obtaining appropriate informed consent.

Patients undergoing emergent/urgent procedures or when there is insufficient time for the parent(s) or legal guardian to fully consider the goals, benefits and risks of this project will not be approached for enrollment.

## Study Description:

This study is a prospective, randomized trial designed to evaluate the role of fibrinogen concentrate versus cryoprecipitate in reducing allogenic donor exposures in infants undergoing cardiac surgery with CPB. Prior to surgery, we will randomize infants undergoing cardiac surgery to receive cryoprecipitate (standard of care) or fibrinogen concentrate (study arm) as part of a post-bypass transfusion algorithm. For patients enrolled in the study, we will follow our standard anesthetic management, cardiopulmonary bypass protocol, and transfusion thresholds in the operating room and ICU.

In each patient, results from our standard of care labs will be obtained at seven different time points:

- 1) Preoperative labs (for outpatients, preoperative baseline labs are obtained in the preoperative clinic; for inpatients, baseline labs are obtained in the hospital the day before surgery) (CBC, Coagulation tests, Fibrinogen, Chemistry),
- 2) After induction of anesthesia but prior to surgical incision (ABG, TEG),
- 3) 10min after initiation of CPB (TEG, Fibrinogen, ABG),
- 4) After termination of CPB, protamine reversal and first cryoprecipitate/FC administration (ABG, TEG, fibrinogen),
- 5) After chest closure or placement of silastic patch if chest remains open (ABG, TEG),
- 6) Coagulation labs on immediate arrival to the ICU as per ICU protocol (ABG, Fibrinogen, Coagulation studies, CBC, Chemistry), and
- 7) On the morning of the first post-operative day in the ICU as per ICU protocol (fibrinogen, ABG, coagulation studies, chemistry, CBC).

Blood samples drawn prior to surgery (i.e time number 1) will be done either by our clinical laboratory for outpatients or by hospital protocol for inpatients. For all other time points, blood samples will be drawn from an indwelling line placed for the surgery.

After separation from bypass, patients will receive either cryoprecipitate or FC, depending on their randomization group. For patients randomized to the study arm, the fibrinogen level measured on bypass will be used to calculate the appropriate dose of fibrinogen concentrate to achieve a level of 300mg/dL after separation from bypass. In these patients, FC will replace cryoprecipitate in our post-bypass transfusion algorithm

for the first dose only. If a patient in either arm continues to have post-bypass bleeding, the anesthesiologist will use point of care testing and the transfusion algorithm to determine appropriate products for transfusion. Patients on the study arm will only receive the initial dose of FC; cryoprecipitate should be used for subsequent low fibrinogen levels.

Data regarding patient demographics, CPB variables, intraoperative and post-operative laboratory values, intraoperative and post-operative transfusion requirements, chest tube output, adverse events, length of ventilation time, ICU and hospital length of stay will be recorded and maintained in a HIPPA secure database.

## Fibrinogen Concentrate (RiaSTAP) Dose:

Hypofibrinogenemia is one of the main reasons for the perioperative coagulopathy in major pediatric surgeries. This hemostatic derangement is amplified in the pediatric population undergoing cardiac surgery due to the hemodilutional effects of the cardiopulmonary bypass machine. Therefore, post-bypass transfusion guidelines often include cryoprecipitate to maintain an adequate fibrinogen level.

Haas et al (10) found that maintaining a higher fibrinogen concentration level (FIBTEM <13mm vs <8mm) significantly decreased bleeding and transfusion requirements for patients undergoing craniosynostosis (median age 10months), but not scoliosis patients (mean age 12 years). Brown et al (7) recently demonstrated that clots formed with neonatal fibrinogen are more porous and less dense than adult clots. The addition of adult fibrinogen to neonatal fibrinogen in higher concentrations creates a more three-dimensional structure than neonatal fibrinogen alone. Using these studies and our historical data that neonates undergoing cardiac surgery had a median post-operative fibrinogen level of 345mg/dL (258-469) (unpublished data), we chose to target a post-transfusion fibrinogen level of 300mg/dL.

Fibrinogen Concentrate (RiaSTAP)

Fibrinogen concentrate can be dosed two ways. For unknown fibrinogen levels, the RiaSTAP dose is 70mg/kg. However, the dose of FC can be calculated to reach a target fibrinogen level.

Dose = (Target Level-Measured Level)/1.7 x weight (kg)

As we have chosen a target fibrinogen level of 300mg/dL, we will use the above equation to calculate the RiaSTAP dose for each patient in the study arm. In order to account for the hemodilutional effects of the bypass prime on fibrinogen levels, the "measured level" will be the fibrinogen level measured after 10min on the CPB machine, time point #2.

Specific Aim #1:

Rational: The goal of Aim #1 is to determine if fibrinogen concentrate can decrease overall allogenic donor exposure in infants undergoing CPB surgery. By targeting a higher level of fibrinogen, we hope to mitigate the effects of the acquired hypofibrinogenemia in post-bypass coagulopathy, while also decreasing the hemodilutional effects of additional blood products during post-bypass transfusion. As massive transfusion in infants is associated with worse outcomes, we hope that reducing transfusions will reduce the short and long term risks associated with allogenic donor exposures.

## Specific Aim #2:

By evaluating the laboratory values, transfusion requirements, and short-term outcomes, we will examine the effectiveness of FC in post-bypass hemostasis. We will evaluate hematocrits, fibrinogen levels, and thrombelastogram values to determine if FC is at least as effective as the standard of care in post-bypass transfusion management. Secondly, we will evaluate secondary outcomes to determine if FC can decrease transfusion related risks such as increased mechanical ventilation, prolonged ICU/hospital stays, infection risks, and thrombosis.

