#### **Significance:**

#### Specific Aim #1:

Demonstrate that fibrinogen concentrate can reduce allogenic donor exposures when compared with cryoprecipitate in infants undergoing cardiac surgery with CPB. The most common cause of post-bypass coagulopathy in infants after bypass surgery is from an acquired hypofibrinogenemia due to hemodilution from the bypass circuit. Secondly, immature neonatal fibringen does not function as well as adult fibringen in forming stable clots. This acquired hypofibrinogenemia is currently treated with cryoprecipitate, a human derived blood product, which requires blood type matching and time to obtain from the blood bank. The FDA has approved fibrinogen concentrate, a lyophilized protein with minimal side effects, for use in pediatric and adult patients with congenital hypofibrinogenemia. Fibrinogen concentrate is being used off-label for treatment of acute acquired hypofibrinogenemia associated with massive bleeding and CPB in pediatric patients. No studies have been done specifically in cardiac surgery patients <12 months, who are most at risk for hypofibrinogenemia due to their small circulating blood volumes, immature coagulation systems, and potential long-term effects of transfusion related risks. Therefore, we have received an IND exemption from the FDA to conduct this randomized, control trial comparing fibrinogen concentrate to cryoprecipitate in hemostatic management of post-bypass coagulopathy in patients <12 months. We propose that replacing cryoprecipitate with reconstituted fibrinogen concentrate will be as effective as cryoprecipitate in treating post-CPB bleeding and decrease total donor exposures by 20%.

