## Sample Size/Statistical Analysis

The primary aim of this study is to determine if fibrinogen concentrate can decrease allogenic donor transfusions in infants undergoing cardiac surgery with cardiopulmonary bypass in patients when compared with the current standard of care, cryoprecipitate. Therefore, we analyzed our blood product transfusion data from CHOA in infants requiring CPB. We counted the number of units of packed red blood cells (PRBCs), fresh frozen plasma (FFP), cryoprecipitate, and platelets the patient received. Each unit was counted as one donor exposure. On average, the patients had nine donor exposures. We propose replacing two units of cryoprecipitate with fibrinogen concentrate will result in a 20% reduction in donor exposures. In order to achieve a power of 0.9, we plan to enroll 15 patients in each arm, for 30 patients at this institution.

The Quantitative Statistical Unit at Stanford University will provide assistance with data management, conducting data analyses, and interpreting statistical results. Continuous variables will be compared by analysis of variance and will be presented as mean  $\pm$  standard variation if normally distributed or by median (IQ range) if non-normally distributed. Nominal variables will be compared by chi-squared analysis or Fisher's exact test. Significance will be defined as a p-value less than or equal to 0.05.

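### Aim 2 asks whether FC is at least as effective as cryoprecipitate, but the plan has only per-protocol tests of difference with no margin, and the primary unit total cannot fill that gap alone

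*Protocol*

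**What the plan says.** **The effectiveness statement.** Protocol Specific Aim #2 (Experimental Design and Methods) says: "We will evaluate hematocrits, fibrinogen levels, and thrombelastogram values to determine if FC is at least as effective as the standard of care". It also names transfusion requirements and short-term outcomes. Specific Aim #1 (Significance) expects that "replacing cryoprecipitate with reconstituted fibrinogen concentrate will be as effective as cryoprecipitate in treating post-CPB bleeding and decrease total donor exposures by 20" per cent.

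**The analysis.** For secondary outcomes the SAP uses a Mann-Whitney test for continuous measures and a chi-squared or Fisher's exact test for categorical ones, all in the per-protocol set. Sensitivity regressions adjust for site, complexity, weight and bypass time. Neither document states a non-inferiority or equivalence margin.

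**The primary outcome.** It is total intraoperative allogenic units, analysed by ITT with linear regression adjusted for institution and complexity. Protocol Sample Size/Statistical Analysis counts red cells, FFP, cryoprecipitate and platelets, one exposure per unit, and gives the expected mechanism: "We propose replacing two units of cryoprecipitate with fibrinogen concentrate will result in a 20% reduction in donor exposures". The SAP Sample Size Justification powers the trial for a reduction of two units.

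**Dosing and sampling.** In the FC arm, "the fibrinogen level measured on bypass will be used to calculate the appropriate dose of fibrinogen concentrate to achieve a level of 300mg/dL". Time point 4 is taken at this stage: "After termination of CPB, protamine reversal and first cryoprecipitate/FC administration (ABG, TEG, fibrinogen". After that, "Patients on the study arm will only receive the initial dose of FC; cryoprecipitate should be used for subsequent low fibrinogen levels". The Protocol also records "intraoperative and post-operative transfusion requirements, chest tube output, adverse events".

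**The concern.** A statement that one treatment is at least as effective as another is a non-inferiority statement. It needs a margin, or at least an interval that a reader can judge. A test of difference that fails to reject in a trial of about 30 per arm shows only that the trial could not tell the arms apart.

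The primary result might seem to fill the gap, since infants who bleed more need more product. But FC takes the place of counted cryoprecipitate units and adds none itself. The total can therefore fall because of the counting rule, with no change in bleeding or in any other product. For donor exposure that fall is the intended benefit. As evidence on hemostasis, it mixes substitution with effect. At stake is a report that reads a lower unit total, or a non-significant laboratory comparison, as proof that FC controls bleeding equally well.

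**Working it through.** **Inputs.** From the SAP Sample Size Justification: control mean 7 units, SD 2.2 in both arms, difference 2, two-sided alpha 0.05, power 90%, 27 per arm, about 10% missing, 30 per arm enrolled. From the Protocol Sample Size section: two cryoprecipitate units replaced.

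**1. Reproduce the plan's figure.** A two-sample t-test with standardised difference 2/2.2 = 0.909 needs 26.4 per arm, rounded up to 27. Power at 27 is 0.906. Allowing for 10% missing, 27/0.9 = 30. The SAP figure reproduces.

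**2. What the primary test detects under substitution.** Let k be the counted cryoprecipitate units that FC replaces and w the extra units of other products needed in the FC arm. The difference in totals is k − w. With k = 2 as planned, and w assumed for illustration:

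| w | Net difference | Power, 27 per arm | Power, 30 per arm |
|---|---|---|---|
| 0 | 2.0 | 0.906 | 0.933 |
| 0.5 | 1.5 | 0.691 | 0.738 |
| 1.0 | 1.0 | 0.374 | 0.410 |

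The row w = 0 is the design itself. The planned power is reached when FC does nothing beyond replacing cryoprecipitate. The documents do not give w, so the lower rows show only that a significant total does not exclude a somewhat higher need for other products.

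**3. What the secondary tests can show.** Setting a margin now would not rescue the claim at this size. With n per arm = 2 × SD² × (1.960 + 1.282)² / margin², an assumed margin of 1 unit, one-sided alpha 0.025, 90% power and no true difference:

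- SD 2.2: 2 × 4.84 × 10.51 / 1 = 101.7, so 102 per arm.
- SD 1.5: 2 × 2.25 × 10.51 / 1 = 47.3, so 48 per arm.

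At 30 per arm the power is about 0.42 and 0.73. The margin and the SD of 1.5 are assumptions.

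**4. Precision of a supportive estimate.** The 95% half-width at 30 per arm is t(0.975, 58) × SD × √(2/30) = 2.002 × SD × 0.258. SD 1.5 gives 0.78, SD 2.2 gives 1.14 and SD 2.5 gives 1.29. The last is close to the SD implied by the reported ITT interval for the total (0.3 to 2.91): half-width 1.305 / 2.003 / 0.258 = 2.52, assuming 30 per arm. The SD of red cell, plasma and platelet units alone is not given.

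**5. Fibrinogen at time point 4.** The FC dose per kg is (300 − measured)/1.7, so the formula predicts measured + 1.7 × dose per kg = 300 mg/dL from any starting level. For an assumed 100 mg/dL, the dose is 200/1.7 = 117.6 mg/kg. Actual recovery and dilution will add scatter. Neither document states a dose rule or target for the control arm, so a between-arm difference here reflects dose as well as product.

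**The case against.** The strongest reply is that the documents never rest effectiveness on the unit total or on one laboratory draw. Aim 2 names several measures, the Protocol schedules TEG and later fibrinogen draws and records chest tube output, and the SAP results claim only fewer units. This stands: the data exist. What is missing is a margin, and an analysis that separates replaced cryoprecipitate from the rest.

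Three stronger readings are tempting, and the documents do not support them.

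- **That the primary outcome is invalid.** Reducing donor exposure is the stated aim, and replaced cryoprecipitate belongs in that count.
- **That time point 4 fibrinogen is only a check on dosing and should be set aside.** The dose is calculated from a sample taken 10 minutes into bypass. Time point 4 follows separation, protamine and the dose, and the Protocol says no study has been done specifically in cardiac surgery patients under 12 months. Whether the formula reaches its target in these infants is an open question. The draw is also closest to the randomised contrast, whereas rescue cryoprecipitate can affect later ones.
- **That the reported ITT reduction of 1.61, being below two, shows FC infants needed more of other products.** Subtracting a constant two leaves 0.39 more units with FC in ITT. Subtracting one leaves 0.61 fewer (1.61 − 1), and in the per-protocol set subtracting two leaves 0.67 fewer (2.67 − 2). The number actually replaced is not given. The ITT set is all enrolled subjects, and the possible per-protocol exclusions include not receiving study medication and not going on bypass, so some infants may have had no substitution. These subtractions are not evidence about the remaining units.

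**Conclusion.** The concern holds as an inference gap in Aim 2. The plan provides per-protocol tests of difference and no margin, so it cannot support a conclusion of at least equal effectiveness. The primary total does not supply that conclusion, because pure substitution of two units alone gives about 91% power (27 per arm, SD 2.2, two-sided alpha 0.05). That figure rests on the SAP's own inputs and the Protocol's expected two-unit replacement. The 69% and 37% figures rest on assumed extra needs of 0.5 and 1 unit. Nothing here indicates that FC was less effective. This is a cheap improvement to interpretation, not a fault in the primary analysis.

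**What to change.** 1. **Add one supportive ITT analysis, labelled post hoc because the SAP already reports results.** Outcome: intraoperative red cell + FFP + platelet units. Use the same linear regression adjusted for institution and complexity, and give the difference with its 95% CI. Show cryoprecipitate units separately by arm, so that rescue use in the FC arm stays visible. Put the per-protocol result and chest tube output beside it. If first and later doses can be separated in the record, also show all units except the first post-bypass cryoprecipitate dose, counting any cryoprecipitate given to FC-assigned infants.
2. **Report Aim 2 laboratory and transfusion differences with confidence intervals.** Do not describe a non-significant difference as showing at least equal effectiveness.
3. **Keep time point 4 fibrinogen as a between-arm comparison.** Add a note that the FC arm was dosed to 300 mg/dL and no control-arm target is stated.

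The cost is one regression and a few sentences, on transfusion data that the Protocol already records. The documents do not say whether first and later cryoprecipitate doses are recorded separately, so the additional display may not be possible. The Aim 2 claim becomes narrower, and the half-width of about 0.8 to 1.3 units means the supportive estimate may be inconclusive.

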## Sample Size/Statistical Analysis

The primary aim of this study is to determine if fibrinogen concentrate can decrease allogenic donor transfusions in infants undergoing cardiac surgery with cardiopulmonary bypass in patients when compared with the current standard of care, cryoprecipitate. Therefore, we analyzed our blood product transfusion data from CHOA in infants requiring CPB. We counted the number of units of packed red blood cells (PRBCs), fresh frozen plasma (FFP), cryoprecipitate, and platelets the patient received. Each unit was counted as one donor exposure. On average, the patients had nine donor exposures. We propose replacing two units of cryoprecipitate with fibrinogen concentrate will result in a 20% reduction in donor exposures. In order to achieve a power of 0.9, we plan to enroll 15 patients in each arm, for 30 patients at this institution.

The Quantitative Statistical Unit at Stanford University will provide assistance with data management, conducting data analyses, and interpreting statistical results. Continuous variables will be compared by analysis of variance and will be presented as mean  $\pm$  standard variation if normally distributed or by median (IQ range) if non-normally distributed. Nominal variables will be compared by chi-squared analysis or Fisher's exact test. Significance will be defined as a p-value less than or equal to 0.05.

### **Adverse Events Reporting**

Monitoring of Adverse Events (AEs) and Serious Adverse Events (SAEs) is an important aspect of data collection. The study subjects will be reviewed on a case-by-case basis. The principal investigator will determine the seriousness of each adverse event and whether or not the event was related to the study.

After enrollment, the principal investigator or designee will collect the adverse experiences from the medical record. Serious adverse Events (life-threatening, requiring intervention) will be reported to the IRB within the guidelines set by the IRB.

The risk of Fibrinogen concentrate administration is low, but adverse events include headache, fever, chills, allergic reaction, or thrombosis. The risks are comparable to the administration of cryoprecipitate.

# **Data Safety Monitoring Plan**

A potential risk of this study is related to drug reactions including fever, chills, headache, allergic reactions, or thrombosis. This medication has been used extensively in Europe and as part of transfusion algorithms around the United States. Based on this data and the need to minimized transfusions in the infant population undergoing cardiac surgery with CPB, the FDA has granted an IND exemption for use of this medication in this randomized, control trial.

The study subjects will be reviewed on a case-by-case basis by the PIs at each institution and quarterly at a committee of experienced cardiac anesthesiologists not involved in the study for review of each study subject for potential adverse events and whether or not the event was related to the study.

A second risk of this study is patient confidentiality since protected health information is included in the study data. This risk will be minimized by only recording information absolutely necessary to fulfill the study's objectives. Information directly identifying patients will be excluded (names, addresses, telephone numbers, social security numbers, email addresses, and account numbers). A unique study number will identify the study subjects. The study information will be collected and stored in a password-protected database. Consents, along with the code linking a subject's identity to an assigned number, will be locked in the office of the principal investigator or designee.

